7.8.3 Additional Efficacy Endpoint(s)

7.8.3.1 Hematocrit, Serum Fe, and Serum Ferritin

Analysis Set: Full Analysis Set

Analysis

Variable(s): HCT

Serum Fe
Serum ferritin
Visit: Baseline , Week 4, 8, 12, 16, 20, 24 and Follow-up
Analytical
Method(s): For each variable, summary statistics will be provided for the observed values and the changes from baseline by treatment group for each visit.

7.8.3.2 Use of Analgesic Medications During the Treatment

Analysis Set: Full Analysis Set
Analysis
Variable(s): Use of analgesic medications during the Treatment from Week 6 to 12
Use of analgesic medications during the Treatment from Week 2 to 6
Use of analgesic medications during the Treatment from Week 18 to 24
Use of analgesic medications during the Treatment for 6 weeks before the final dose
Analytical
Method(s): For each variable, summary statistics will be provided by treatment group.

7.8.3.3 WPAI:GH During the Treatment

Analysis Set: Full Analysis Set
Analysis
Variable(s): Absenteeism
Presenteeism
Work productivity loss
Activity impairment
Visit: Baseline , Week 2, 4, 8, 12 and 24
Analytical
Method(s): For each variable, summary statistics will be provided for the observed values and the changes from baseline by treatment group for each visit. The mean differences in the observed values between TAK-385 40 mg and leuprorelin group and the two-sided 95% confidence intervals will be provided for each visit.

7.8.3.4 Amenorrhea (The subject with a total PBAC score of 0)

Analysis Set: Full Analysis Set

Analysis

Variable(s): Proportion of subjects with a total PBAC score of 0 from Week 6 to 12
Proportion of subjects with a total PBAC score of 0 from Week 2 to 6
Proportion of subjects with a total PBAC score of 0 from Week 18 to 24
Proportion of subjects with a total PBAC score of 0 for 6 weeks before the final dose of study drug

Analytical

Method(s): For each variable, frequency will be summarized by treatment group.
The point estimate and 2-sided 95% confidence interval of the difference in the percentage will be calculated between TAK-385 40 mg group and leuprorelin group, using FM method with the non-inferiority margin of -15%. The confidence interval will be presented in a descriptive manner and not for the purpose of statistical inference.

7.9 Pharmacokinetic/Pharmacodynamic Analysis

7.9.1 Pharmacokinetic Analysis

Not applicable

7.9.2 Pharmacodynamic Analysis

7.9.2.1 LH, FSH, E₂, and P

Analysis Set: Full Analysis Set

Analysis

Variable(s) : LH
FSH
E₂
P

Visit: Baseline , Week 2, 4, 8, 12, 16, 20, 24 and Follow-up

Analytical

Method(s) : For each variable, summaries (1) and (2) will be provided by treatment group.

- (1) Summary of each variable and Change from Baseline by Visit
Descriptive statistics for observed values for each visit and changes from baseline will be provided.
- (2) Case Plots
Plots over time for each subject will be presented.

7.10 Other Outcomes

Not applicable

7.11 Safety Analysis

7.11.1 Adverse Events

7.11.1.1 Overview of Treatment-Emergent Adverse Events

Analysis Set: Safety Analysis Set

Analysis

Variable(s) : Treatment-emergent adverse event (TEAE)

Categories: Relationship to Study Drug [Related, Not Related]

Intensity [Mild, Moderate, Severe]

Analytical

Method(s) : The following summaries will be provided for each treatment group.

- (1) Overview of Treatment-Emergent Adverse Events
 - 1) All Treatment-Emergent Adverse Events (number of events, number and percentage of subjects)
 - 2) Relationship of Treatment-Emergent Adverse Events to study drug (number of events, number and percentage of subjects)
 - 3) Intensity of Treatment-Emergent Adverse Events (number of events, number and percentage of subjects)
 - 4) Treatment-Emergent Adverse Events leading to study drug discontinuation (number of events, number and percentage of subjects)
 - 5) Serious Treatment-Emergent Adverse Events (number of events, number and percentage of subjects)
 - 6) Relationship of serious Treatment-Emergent Adverse Events to

study drug (number of events, number and percentage of subjects)

- 7) Serious Treatment-Emergent Adverse Events leading to study drug discontinuation (number of events, number and percentage of subjects)
- 8) Treatment-Emergent Adverse Events resulting in death (number of events, number and percentage of subjects)

TEAEs will be counted according to the rules below.

Number of subjects

- Summaries for 2) and 6)
A subject with occurrences of TEAE in both categories (ie, Related and Not Related) will be counted once in the Related category.
- Summary for 3)
A subject with multiple occurrences of TEAE will be counted once for the TEAE with the maximum intensity.
- Summaries other than 2) , 3) , and 6)
A subject with multiple occurrences of TEAE will be counted only once.

Number of events

For each summary, the total number of events will be calculated.

7.11.1.2 Displays of Treatment-Emergent Adverse Events

Analysis Set: Safety Analysis Set

Analysis

Variable(s) : TEAE

Categories: Intensity [Mild, Moderate, Severe]

Time of Onset (day) [1<= - <=28, 29<= - <=56, 57<= - <=84, 85<= - <=112, 113<= - <=140, 141<= - <=168, 169<= - <=Max]

Analytical

Method(s) : The following summaries will be provided using frequency distribution

for each treatment group.

TEAEs will be coded using the MedDRA and will be summarized using SOC and PT.

SOC will be sorted alphabetically and PT will be sorted in decreasing frequency for tables provided by SOC and PT. SOC and PT will be sorted in decreasing frequency for tables provided by System Organ Class only or PT only.

- (1) Treatment-Emergent Adverse Events by System Organ Class and Preferred Term
- (2) Treatment-Emergent Adverse Events by System Organ Class
- (3) Treatment-Emergent Adverse Events by Preferred Term
- (4) Drug-Related Treatment-Emergent Adverse Events by System Organ Class and Preferred Term
- (5) Intensity of Treatment-Emergent Adverse Events by System Organ Class and Preferred Term
- (6) Intensity of Drug-Related Treatment-Emergent Adverse Events by System Organ Class, and Preferred Term
- (7) Treatment-Emergent Adverse Events Leading to Study Drug Discontinuation by System Organ Class and Preferred Term
- (8) Serious Treatment-Emergent Adverse Events by System Organ Class and Preferred Term
- (9) Treatment-Emergent Adverse Events by System Organ Class and Preferred Term Over Time
- (10) Most Frequent Treatment-Emergent Adverse Events by System Organ Class and Preferred Term
- (11) Most Frequent Non-Serious Treatment-Emergent Adverse Events by System Organ Class and Preferred Term

The frequency distribution will be provided according to the rules below.

Number of subjects

- Summary tables other than (5), (6) and (9)

A subject with multiple occurrences of TEAE within a SOC will be counted only once in that SOC. A subject with multiple occurrences of TEAE within a PT will be counted only once in that PT.

Percentages will be based on the number of subjects in the safety analysis set.

- Summary tables for (5) and (6)

A subject with multiple occurrences of TEAE within a SOC or a PT will be counted only once for the TEAE with the maximum intensity.

Percentages will be based on the number of subjects in the safety analysis set.

- Summary table for (9)

A subject with a TEAE that occurs in more than one interval is counted in all the intervals that the TEAE occurs. For each time interval, a subject with multiple occurrences of TEAE within a SOC or a PT will be counted only once in that SOC or PT.

When calculating percentages for each time interval, the number of subjects at risk (ie, subjects who either have an exposure or have an occurrence of TEAE, during or after the corresponding time interval) will be used as the denominator. The number of subjects whose onset of any one of the TEAEs is within the time interval will be used as the numerator.

- Summary table for (10)

Most frequent TEAEs refer to PTs whose percentages are at least 5.0% in any one of the treatment groups.

- Summary table for (11)

Most frequent Non-Serious TEAEs refer to PTs whose percentages are at least 5.0% in any one of the treatment groups. If no Non-Serious TEAEs exceed a frequency of 5.0%, the frequency cutoff of 2.0% will be used instead. Percentages will be based on the number of subjects in the safety analysis set.

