4.0 INTRODUCTION

4.1 Background

Uterine fibroid is a benign sex hormone-dependent gynecological disease affecting 1 in every 3 to 4 women. Most uterine fibroids are asymptomatic, but clinical symptoms such as increase in menstrual blood loss and anemia due to menorrhagia as well as compression and pain in the bladder and pelvis due to large myoma are seen in about 10% to 20% of patients. In particular, menorrhagia is considered to be caused by the combination of an increase in surface area of the uterine cavity; poor uterine contraction due to myoma; and increased circulation, congestion, or impaired hemostasis due to hypertrophy of the endometrium in the vicinity of the myoma. Persistent menorrhagia is known to induce iron-deficiency anemia. Therefore, menorrhagia is a primary factor that deteriorates the quality of life (QOL) of patients with uterine fibroids.

Gonadotropin-releasing hormone (GnRH) agonists, such as leuprorelin are commonly used for the treatment of benign sex hormone-dependent gynecological diseases, such as endometriosis and uterine fibroids. It is considered that continuous use of a GnRH agonist induces a transient increase in the secretion of gonadotropins (flare up), followed by pituitary and gonadal desensitization that decreases sex hormone secretion. Therefore, GnRH agonists exert therapeutic effects against these diseases by reducing secretion of sex hormones. However, GnRH agonists often cause flare up (temporary worsening of symptoms) and may typically take about 3 to 4 weeks before therapeutic effects begin to emerge. They also cannot be orally administered because they are peptides. For these reasons, the development of a new oral drug that is not associated with temporal worsening of symptoms is awaited for the treatment of these diseases.

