4.2 Rationale for the Proposed Study

A phase 1 study

[REDACTED]

The efficacy and safety of TAK-385 were investigated when orally administered to patients with uterine fibroids at dose levels of 10, 20, and 40 mg for 12 weeks, compared to placebo in the Phase 2 study (TAK-385/CCT-001).

In the efficacy evaluation, a statistically significant difference in proportion of subjects with a total pictorial blood loss assessment chart (PBAC) score of < 10 from Week 6 to 12, as the primary endpoint in the Phase 2 study, was observed between each TAK-385 group and placebo group. The proportion was highest in TAK-385 40 mg group, suggesting a dose-response relationship. The decrease in menstrual blood loss, and achievement of amenorrhea, being ones of the secondary endpoints in this study, was seen in higher proportion of subjects at the higher dose levels of TAK-385 evaluated.

In the safety evaluation, the common treatment-emergent adverse events (TEAEs) reported during the study period were nasopharyngitis, headache, metrorrhagia, menorrhagia (among the 35 subjects in which the symptoms were categorized as menorrhagia, 34 subjects were actually diagnosed with menostaxis [lowest level term].), genital hemorrhage, menstruation irregular and hot flush. As for the TEAEs relevant to the pharmacological activity of TAK-385, such as hot flush, headache, menstruation irregular, and metrorrhagia, the incidence was higher in accordance with the dose levels among the 10, 20, and 40 mg groups of TAK-385, but there were no clinically significant TEAEs related to the study drug. The percent change of bone mineral density (BMD) in this study was considered to be the same level compared to the percent change of BMD that has previously been reported with the use of leuprorelin 3.75 mg.

Based on the above, a Phase 3 confirmatory study in uterine fibroid patients was planned to investigate the efficacy and safety of TAK-385 40 mg compared to leuprorelin which is widely used for the treatment of uterine fibroids.

Pharmacogenomics (PGx) analysis may be conducted to investigate the contribution of genetic variance on drug response, eg, its efficacy and safety. Participation of study subjects in PGx sample collection is optional.

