9.1.16 PBAC

The volume of menstrual blood loss is measured using the PBAC score. The investigator or subinvestigator distributes the patient diary to consented subjects. Subjects fill out the patient diary every day from VISIT 1 to the day before VISIT 10 (or until early termination).

From VISIT 1, subjects are required to use only the sanitary products designated by the sponsor. The products supplied by the study site are shown below:

- Sanitary towel (pad): [REDACTED]
- Tampon: [REDACTED]

Products other than those supplied by the study site may only be used outside the menstruation period to prevent staining of the underwear. However, those sanitary products supplied by the study site must be immediately used when bleeding is observed.

Subjects should check the sanitary product after use, and record the number of used products that look similar to each of the diagrams of the sanitary towel or tampon in the PBAC sheet every day.

The investigator or subinvestigator should check the recorded PBAC scores at each subject's visit. Additionally, the start/end date of menstruation must be recorded in CRF in reference to the PBAC score. If there is anything unclear or insufficient description in the patient diary, queries may be made to the subject, and corrections to the patient diary are recorded by the subject in an change history that captures the old information, the new information, identification of the person making the correction and the date the correction. If it is impossible to make queries to the subject at site visits, queries will be made to the subject with telephone calls or other means, and corrections to the patient diary are recorded by the investigator or subinvestigator in a change history that captures the old information, the new information, identification of the person making the correction and the date of the correction.

Three diagrams each for the sanitary towel and tampon are shown in the PBAC score sheet. Each diagram represents a lightly stained, moderately stained, or completely saturated pad or tampon. The following scores are assigned to these categories:

- Add 1, 5, or 20 points for each lightly stained, moderately stained, or completely saturated pad, respectively.
- Add 1, 5, or 10 points for each lightly stained, moderately stained, or completely saturated tampon, respectively.
- Add 1 or 5 points for each blood clot of smaller than 1 cm or for each blood clot of 1 cm or larger in the longest diameter, respectively.

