- Insufficient clinical response, efficacy, or pharmacologic action, should NOT be recorded as an AE. The investigator or subinvestigator must make the distinction between exacerbation of pre-existing illness and lack of therapeutic efficacy.

Overdose:

- Cases of overdose with any medication without manifested side effects are NOT considered AEs, but instead will be documented on an Overdose page of the eCRF. Any manifested side effects will be considered AEs and will be recorded on the AE page of the eCRF.

Worsening of the target disease:

- Worsening of expected conditions (measured by the primary efficacy and other endpoints) within the normal course will not be recorded as AEs.

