13.1.5 Safety Analysis

The following analyses will be based on the safety analysis set.

(1) Secondary endpoint

Treatment-emergent adverse events

A TEAE is defined as an AE whose date of onset occurs on or after the start of study drugs for the Treatment.

TEAEs will be coded using the MedDRA dictionary. The frequency distribution will be provided using the system organ class (SOC) and the preferred term (PT) for each treatment group as follows:

- All TEAEs
- Drug-related TEAEs
- Intensity of TEAEs
- Intensity of drug-related TEAEs
- TEAEs leading to study drug discontinuation
- Serious TEAEs
- TEAEs over time

Laboratory test results, standard 12-lead ECGs, vital signs, weight, BMD and biochemical bone metabolism markers (serum NTELOP and BAP)

For continuous variables except BMD, the observed values and the changes from baseline will be summarized by treatment group for each visit using descriptive statistics. For BMD, the observed values and the percent changes from baseline will be summarized by treatment group for each visit using descriptive statistics. Case plots will also be presented for the observed values.

For categorical variables, shift tables showing the number of subjects in each category at baseline and each post-baseline visit will be provided for each treatment group.

(2) Additional endpoint

- Period from the last dose of study drug to return of menstrual cycles.

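### TEAE tables stop at preferred term, so the Menorrhagia row may present prolonged bleeding as heavy bleeding, as the sponsor found in phase 2

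*SAP*

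**What the plan says.** Both documents set the same display level. Protocol 13.1.5 says of TEAEs: "The frequency distribution will be provided using the system organ class (SOC) and the preferred term (PT) for each treatment group as follows". SAP 7.11.1.2 says: "TEAEs will be coded using the MedDRA and will be summarized using SOC and PT". The SAP then lists tables (1) to (11). These vary by relatedness, intensity, seriousness, time of onset and frequency, but none uses LLT. Within a PT, a subject is counted once; table (9) applies this per time interval.

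Protocol 4.2 names menorrhagia among the common phase 2 TEAEs and qualifies it at once: "among the 35 subjects in which the symptoms were categorized as menorrhagia, 34 subjects were actually diagnosed with menostaxis", with a bracketed note that this is the lowest level term.

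Two further provisions bear on how the row will be read. Menorrhagia is the entry condition (inclusion criterion 11, total PBAC of at least 120 in the cycle before VISIT 3). And Protocol 10.1.2 says: "Worsening of expected conditions (measured by the primary efficacy and other endpoints) within the normal course will not be recorded as AEs".

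**The concern.** The sponsor needed the LLT to explain its own phase 2 table, and the phase 3 plan keeps the display that needed explaining. All subjects enter with menorrhagia, and ordinary worsening of it is not an AE. A reader who meets a frequent Menorrhagia row will therefore take it as heavy bleeding beyond the normal course. Phase 2 suggests it would mostly be menostaxis, that is, prolonged bleeding.

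At stake is a correct description of a common TEAE, and whether prolonged and heavy bleeding can be told apart by arm in the AE tables. No test or decision rule depends on it.

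**Working it through.** **1. The phase 2 count.** Inputs from Protocol 4.2: 35 subjects categorized as menorrhagia, 34 of them menostaxis at LLT. Share = 34/35 = 97.1%. Exact (Clopper-Pearson) limits: lower = 2.5% quantile of Beta(34, 2) = 85.1%; upper = 97.5% quantile of Beta(35, 1) = 99.9%. One subject of 35 had something else. The protocol does not name the level of the menorrhagia category; I read it as PT because it is contrasted with the LLT.

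**2. What other planned displays cover.**

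| Display | What it shows by arm | What it leaves out |
|---|---|---|
| PBAC < 10 (SAP 7.8.1, 7.8.2.1) and PBAC = 0 (SAP 7.8.3.4) | Low or no blood loss in Day 15–42, 43–84, 127–168 and the last 42 days of treatment | Duration; any cut-off above 10; Day 1–14 |
| Hemoglobin (SAP 7.8.2.3) | Consequence of blood loss, from Week 4 | Duration and pattern of bleeding |
| Intensity by PT, table (5) | Mild, moderate, severe, defined in Protocol 10.1.5 by tolerance and effect on activities | Long versus heavy bleeding |
| Onset over time, table (9) | First interval Day 1–28 | Anything below PT |

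PBAC sums a score over a window, so it does not describe duration, which is what marks menostaxis. Protocol 9.1.16 has menstruation start and end dates recorded in the CRF, but the SAP plans no analysis of bleeding duration. For a subject who completes treatment, the last 42 days coincide with Day 127–168, so Day 1–14 and Day 85–126 have no PBAC summary by arm. Treatment starts on the first to fifth day of a menstruation, and Protocol 4.1 expects an agonist flare before effects emerge at about 3 to 4 weeks. Table (9) is the planned bleeding display that takes in Day 1–14, and it stops at PT.

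**3. What one PT row can conceal (illustration only).** Assume 144 subjects per arm (Protocol 13.3), the same share with PT Menorrhagia in both arms, and 97% of these menostaxis in arm A. The PT shares and the arm B splits are my assumptions; the documents give neither.

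Subjects with another LLT = (subjects with the PT) × (1 − menostaxis share); the percentage divides by 144.

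| PT share, both arms | Subjects per arm | Arm A, 97% menostaxis | Arm B, 97% | Arm B, 80% | Arm B, 50% |
|---|---|---|---|---|---|
| 20% | 29 | 0.9 (0.6%) | 0.9 (0.6%) | 5.8 (4.0%) | 14.5 (10.1%) |
| 40% | 58 | 1.7 (1.2%) | 1.7 (1.2%) | 11.6 (8.1%) | 29.0 (20.1%) |
| 60% | 86 | 2.6 (1.8%) | 2.6 (1.8%) | 17.2 (11.9%) | 43.0 (29.9%) |

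For example, 58 × 0.20 = 11.6, and 11.6/144 = 8.1%. In every line the PT rows of the two arms are identical. If the split is the same in both arms, no difference is concealed and only the row's name misleads.

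**The case against.** The strongest case against is that AE coding is not how this trial measures bleeding. Protocol 9.1.16 says: "The volume of menstrual blood loss is measured using the PBAC score". PBAC and hemoglobin are compared by arm, and discontinuations for lack of efficacy and for reduced hemoglobin are tabulated by arm (SAP 7.3.5). Protocol 10.1.2 limits how much heavy bleeding reaches the AE data at all, and 34 of 35 describes a row that is nearly all one thing, not a mixture. The AE tables are descriptive, and the sponsor could add an LLT note in the study report, as it did in Protocol 4.2.

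Much of this stands. A reader might infer that the plan hides which arm bled heavily, or that the bleeding comparison cannot be interpreted. The documents do not support either, because of the PBAC and hemoglobin analyses. Nor do they support a presumed difference between arms in the LLT split: phase 2 compared TAK-385 doses with placebo, had no leuprorelin arm, and Protocol 4.2 does not divide the 35 subjects by group. An inference that a product label would carry the wrong term has no basis in them. Extending the breakdown to metrorrhagia, genital hemorrhage or menstruation irregular is not supported either, since an LLT problem is reported for one PT only.

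What the objection does not remove is the naming problem. A row that is nearly all menostaxis under the heading Menorrhagia is misdescribed, and no other planned table shows prolonged bleeding by arm. A note written after unblinding is possible, but the ambiguity is already known and can be settled beforehand.

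**Conclusion.** The point holds as a minor reporting gap. Followed exactly, the plan would probably label prolonged bleeding with the name of the entry symptom, and its AE tables could not separate prolonged from heavy bleeding by arm. The evidence is the phase 2 share alone; no phase 3 figure can be derived.

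The conclusion assumes that phase 3 coding maps menostaxis to the same PT. That cannot be confirmed: SAP 7.3.1 says only that the MedDRA version will be reported. The Handling Rules for Analysis Data were not available, and SAP 7.1.4 provides for data listings without stating the level of the AE term. SAP and protocol agree on SOC and PT, so there is no conflict between them. The primary endpoint, sample size, significance level and non-inferiority conclusion are untouched.

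**What to change.** In SAP 7.11.1.2, before unblinding, add an LLT breakdown under PT Menorrhagia by treatment group, at least in tables (1) and (9): one sub-row for menostaxis and one for all other LLTs. State that a subject with both is counted once in each, so the sub-rows can add up to more than the PT row. Add a footnote referring to the PBAC results (SAP 7.8.1, 7.8.2.1 and 7.8.3.4) for the amount of blood loss. The PT rows stay, so the display remains consistent with Protocol 13.1.5.

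The cost is one SAP line and a few extra table rows. Protocol 4.2 shows that LLTs were available in phase 2 coding; the sponsor should confirm the same for this study. Blind review has already led to several display changes in SAP 7.13, so an addition of this kind is proportionate.
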